6.3 Safety Assessments

Adverse Events

The Investigator and study personnel will monitor each patient for AEs occurring throughout the study treatment period. The process of collection and reporting of AEs is described in Section 6.3.1.

Vital Signs

Vital sign measurements will be taken after the patient has been resting in the sitting position for at least 5 minutes and will include diastolic and systolic blood pressure and heart rate. Vital signs may be repeated if clinically significant values are measured. Out-of-range blood pressure or heart rate measurements will be repeated at the Investigator’s discretion especially if the investigator believes that the initial measurements are due to insufficient relaxation or error. Any confirmed, clinically significant vital sign measurements must be recorded as AEs.

Electrocardiogram (ECG)

A single 12-lead ECG will be collected after a 5-minute period of rest and should be completed before any blood collection. If any clinically significant changes in findings are observed versus the predose or baseline visits, they must be documented. If a clinically significant abnormal finding occurs after the patient initiates use of the study drug, then it will be recorded as an AE in the eCRF.

IIEF

The IIEF is a validated 15-item questionnaire that was designed to evaluate sexual function in men with possible erectile dysfunction. The main purpose of including this instrument in this study is to exclude men with coexisting erectile dysfunction at baseline and to check whether erectile dysfunction occurs during the study.¹⁶ As this instrument was designed for use in men with possible erectile dysfunction, the investigator should clarify the meaning of Questions 4, 5, and 15 before the patient completes the questionnaire. The patient should be told that he is being asked to assess whether he can maintain his erection until ejaculation occurs (Questions 4 and 5) and about his confidence to get and keep an erection until ejaculation occurs (Question 15).

Psychological Assessments

The following questionnaire will be self-completed by each patient using the LogPad (e-diary).

- Patient Health Questionnaire (PHQ-9)

The PHQ-9 is a reliable and valid screening tool for depression severity. The module scores each of the 9 Diagnostic and Statistical Manual of Mental Disorders, fourth edition (DSM-IV) criteria as “0” (not at all) to “3” (nearly every day). A PHQ-9 score ≥ 10 had a sensitivity of 88% and a specificity of 88% for major depression. PHQ-9 scores of 5, 10, 15, and 20 represented mild, moderate, moderately severe, and severe depression, respectively.¹⁷ The questionnaire will be completed at each study visit during the treatment period.

The Investigator will administer the following instrument at baseline and at other times thereafter throughout the study as required by the protocol.

- C-SSRS

The C-SSRS is a structured clinical interview used to assess an individual’s behavior to exhibit thoughts or intent to commit suicide.¹⁸ Investigators and other designated staff performing the interview must be trained in its use.

6.3.1 Adverse Events

6.3.1.1 Definitions of Adverse Events

An AE is any untoward medical occurrence in a patient administered a pharmaceutical product and that does not necessarily have a causal relationship with this treatment. An AE can therefore be any unfavorable and unintended sign (including an abnormal laboratory finding), symptom, or disease temporally associated with the use of a medicinal (investigational) product, whether or not related to the medicinal (investigational) product. Lack of drug effect is not an AE in clinical studies because the purpose of the clinical study is to establish drug effect. After the informed consent form (ICF) is signed, site personnel will record any change in the condition(s) and the occurrence and nature of any AEs.

An SAE or serious adverse drug reaction is any untoward medical occurrence at any dose that:

- results in death;
- is life threatening (immediate risk of death);
- requires inpatient hospitalization or prolongation of existing hospitalization;
- results in persistent or significant disability/incapacity;
- results in a congenital anomaly/birth defect.

An SAE may also be any other medically important event that, in the opinion of the Investigator, may jeopardize the patient or may require intervention to prevent one of the other outcomes listed in the definition above. (Examples of such medical events include allergic bronchospasm requiring intensive treatment in an emergency room or convulsions occurring at home that do not require an inpatient hospitalization).

Serious adverse event collection begins after the patient has signed informed consent and has received investigational product through to 28 calendar days after last administration of the investigational product.

Planned surgeries should not be reported as SAEs unless the underlying medical condition has worsened during the course of the study.

The investigator does not need to actively monitor patients for AEs once the study has ended (after follow-up visit), unless stipulated otherwise in the protocol. However, if an investigator becomes aware of any SAEs occurring after the patient's participation in the study has ended, the investigator should report the SAEs to Ixcelsius or designated representative regardless of the investigator's opinion of causation. In order to adhere to all applicable laws and regulations for reporting an SAE, the study site must notify Ixcelsius or designated representative within 24 hours of the study site staff becoming aware of the SAE.

6.3.1.2 Eliciting and Documenting Adverse Events

For all AEs, the investigator must pursue and obtain information adequate to determine the outcome of the AE and to assess whether it meets the criteria for classification as an SAE requiring immediate notification to Ixcelsius or designated representative. For all AEs, sufficient information should be obtained by the investigator to determine the causality of the AE.

6.3.1.3 Reporting Adverse Events

All observed AEs and their suspected causal relationship to the study product will be reported. Adverse events and SAEs should be reported using concise medical terminology as appropriate in the eCRF.

For all AEs, the Investigator must obtain information adequate both to determine the outcome of the AE and to assess whether it meets criteria for classification as an SAE requiring immediate notification to Ixcelsius or designated representative.

If an SAE occurs, expedited reporting to regulatory authorities will follow local regulations, as appropriate. The Investigator must report all SAEs to Ixcelsius or designated representative within 24 hours of the Investigator's awareness of the event. This timeframe also applies to additional new information on previously reported SAEs. The contact details for reporting SAEs by telephone and fax are as follows:

PPD 24-Hour Safety [contact]

PPD 24-Hour Safety Hotline [contact]

6.3.1.4 Assessment of Severity

Severity describes the intensity of a specific event:

- Mild – Symptom(s) barely noticeable to the patient or does not make the patient uncomfortable. The AE does not influence performance or functioning. Prescription drugs are not ordinarily needed for relief of symptom(s).
- Moderate – Symptom(s) of a sufficient severity/intensity to make the patient uncomfortable. Performance of daily activities is influenced. Treatment of symptom(s) may be needed.
- Severe – Symptom(s) of a sufficient severity to cause the patient severe discomfort. Severity may cause cessation of treatment with the investigational product. Treatment for symptom(s) may be given.
- Life-threatening – Symptom(s) of a sufficient severity/intensity to cause the patient to be at immediate risk of death. Treatment for symptom(s) may be given.

6.3.1.5 Assessment of Causality

For all AEs, sufficient information should be obtained by the Investigator to determine the causality of the AE (serious and nonserious). An Investigator's causality assessment is the

determination of whether there exists a reasonable possibility that the study product caused or contributed to an AE. If the Investigator's final determination of causality is unknown because the Investigator does not know whether or not the study product caused the AE, then the AE will be handled as "related to investigational product" for reporting purposes and reporting expedited according to local regulations. If the Investigator's final determination of causality is "unknown but not related to investigational product," this information should be clearly documented in the study records.

In addition, if the Investigator determines that an SAE is associated with study procedures, the Investigator must record this causal relationship in the source documents and eCRF, as appropriate, and report such an assessment in accordance with the SAE reporting requirements, if applicable.

6.3.1.6 Follow-Up of Patients Reporting Adverse Events

For all AEs, follow up by the Investigator is required until the event or its sequelae resolve or stabilize at a level acceptable to the Investigator. The medical monitor will monitor safety data throughout the course of the study.

6.4 Pregnancy

If the partner of a patient is of childbearing potential, then at least one reliable form of contraception must be used.

If a patient used condoms during the run-in period when engaging in sexual intercourse, then he must continue to use the same brand and type of condom for every sexual intercourse attempt. If the condom is the main method of contraception, then it should be used with spermicide (or similar product according to availability). If the patient did not use a condom during the run-in period, then his partner must use a form of contraception such as intrauterine device, diaphragm with spermicide (or similar product according to availability), oral contraceptives, injectable progesterone, subdermal implants, or tubal ligation when engaging in sexual intercourse, unless the patient has had a documented vasectomy or confirmed azoospermia.

This criterion must be followed from the time of the run-in period until 30 days after the last dose of study medication.

If a patient reports that his partner is pregnant, the patient must be withdrawn from the study and the Investigator will inform Ixcelsius or designee, who will endeavor to collect any relevant information on the outcome of the pregnancy unless there is confirmation that the patient was not exposed to study drug prior to or during the pregnancy. Cases of pregnancy that occur after a patient has been consented should be reported. Data on fetal outcome and breastfeeding will be collected for regulatory reporting and drug safety evaluation.

The Investigator must report the pregnancy to Ixcelsius or designee with 24 hours of the study site staff becoming aware of the pregnancy.

6.5 Laboratory Analyses

The central laboratory will process all samples collected for laboratory safety function tests. Section 13.3 provides a full list of tests, and the details regarding the laboratory safety tests and sampling can be found in the Study Training Manual.

Collection of blood and urine samples for clinical laboratory analysis will occur per the Schedule of Events (Table 13-1). Whole blood samples will be collected at each of these time points for hematology and clinical chemistry with coagulation testing being performed at baseline. An additional collection of blood sample for serology testing (hepatitis B surface antigen, hepatitis C virus antibody, HIV 1, HIV 2) will be performed at screening only.

Urine samples will be collected for urinalysis (Screening, Visit 2, Visits 4-6) and urine drug screen (Screening, Visit 2 and Visit 5 only).

7 Statistical and Analytical Plan

7.1 Primary Efficacy Endpoint

The primary efficacy endpoint of this study is the change in GM IELT over the treatment assessment period compared with baseline, ie, $[GM(IELT_{\text{treatment period}}) - GM(IELT_{\text{baseline}})]$.

7.2 Secondary Efficacy Endpoints

7.2.1 Key Secondary Efficacy Endpoints

The following key secondary efficacy endpoints will be analyzed:

1. Fold change in GM IELT over the treatment assessment period compared with baseline.
2. Proportion of patients with ≥ 2.5 -fold increase in GM IELT over the treatment assessment period compared with baseline, ie, $[\text{proportion of subjects with } GM(IELT_{\text{treatment period}})/GM(IELT_{\text{baseline}}) \geq 2.5]$.
3. Proportion of patients rating their PE as improved per the CGIC questionnaire.
4. Proportion of patients achieving mean change in category of ≥ 1 or ≥ 2 on control of timing of ejaculation (PEP), ie, improving control from “very poor” or “poor” to “fair,” “good,” or “very good” at end of treatment.
5. Proportion of patients achieving mean change in category of ≥ 1 or ≥ 2 in ejaculation-related personal distress (PEP), ie, improving rating of ejaculation-related distress to “moderate,” “a bit,” or “not at all” at end of treatment.
6. Proportions of patients achieving change in category of ≥ 2 on control of timing of ejaculation (PEP) and achieving change in category of ≥ 1 in ejaculation-related personal distress (PEP) at end of treatment
7. Mean change from baseline in score on control of ejaculation (e-diary) over the treatment assessment period.
8. Mean change from baseline in score on ejaculation-related personal distress (e-diary) over the treatment assessment period.

7.2.2 Other Secondary Efficacy Endpoints

The following other secondary efficacy endpoints will be analyzed:

1. Fold change from baseline in (arithmetic) mean IELT over the treatment assessment period.
2. Change from baseline in (arithmetic) mean IELT over the treatment assessment period.
3. Proportion of patients with GM IELT of ≥ 1 minute over the treatment assessment period.
4. Proportion of patients with GM IELT of ≥ 2 minutes over the treatment assessment period.
5. Proportion of patients with GM IELT of ≥ 3 minutes over the treatment assessment period.
6. Proportion of patients with GM IELT of ≥ 4 minutes over the treatment assessment period.
7. Proportion of patients with GM IELT of ≥ 5 minutes over the treatment assessment period.
8. Proportion of patients with GM IELT increase over the treatment assessment period of ≥ 45 seconds compared with baseline.
9. Proportion of patients with GM IELT increase over the treatment assessment period of ≥ 1 minute compared with baseline.
10. Percentage of intercourse attempts lasting > 1 minute over the treatment assessment period.
11. Percentage of intercourse attempts lasting > 2 minutes over the treatment assessment period.
12. Percentage of intercourse attempts lasting > 3 minutes over the treatment assessment period.
13. Percentage of intercourse attempts lasting > 4 minutes over the treatment assessment period.
14. Percentage of intercourse attempts lasting > 5 minutes over the treatment assessment period.
15. Proportion of patients improving on PGIS
16. Proportion of patients achieving ≥ 1 category of improvement from baseline to end of treatment in each of the following (from 4-weekly PEP questionnaire):

- a. Satisfaction with sexual intercourse
 - b. Control over ejaculation during sexual intercourse
 - c. Ejaculation-related distress
 - d. Ejaculation-related interpersonal difficulty
 - e. Ejaculation-related bother
17. Change in score from baseline in each of the following (from 4-weekly PEP questionnaire):
- a. Satisfaction with sexual intercourse
 - b. Control over ejaculation during sexual intercourse
 - c. Ejaculation-related distress
 - d. Ejaculation-related interpersonal difficulty
 - e. Ejaculation-related bother

7.3 Sample Size Calculations

The target total is for 220 patients to be randomized in the study.

The randomization ratio will be 2:2:3:3 (placebo, IX-01 400 mg, IX-01 800 mg, and IX-01 1200 mg dose groups, respectively).

Thus, 44 patients each will be randomized to placebo and IX-01 400 mg dose groups, and 66 patients each will be randomized to IX-01 800 mg and IX-01 1200 mg dose groups. The 2:3 ratio results in only slight loss of statistical power from 1:1 randomization, while increasing the chances that a patient will be randomized to an effective dose of study drug.

Assuming an alpha (2-sided) of 0.05 and an SD of 70 seconds, a sample size of 220 patients randomized in total (44 to the placebo and IX-01 400 mg dose groups and 66 to the IX-01 800 mg and IX-01 1200 mg dose groups) provides approximately 85%, 90%, and 90% power to detect a mean difference of 45 seconds between change from baseline in GM of IELT for the IX-01 400 mg, IX-01 800 mg, and IX-01 1200 mg dose groups, respectively, compared with the placebo group.

Sequential multiplicity control testing of IX-01 1200 mg dose versus placebo, followed by IX-01 800 mg dose versus placebo and then IX-01 400 mg dose versus placebo will be done in order to control for multiplicity. See details below.

Additional patients may be recruited if some patients discontinue from the study with less than 2 postbaseline IELT assessments.

7.4 Analysis Sets

The following 4 populations, defined as below, will be used in the analyses:

Intent-to-Treat (ITT) Set: The ITT Set is defined as all randomized patients who have taken at least 1 dose of study medication. Patients will be analyzed according to the treatment arm to which they were randomized.

Modified Intent-to-Treat (mITT) Set: The mITT Set is defined as all randomized patients who have taken at least 1 dose of study medication and with at least 2 postbaseline analyzable IELT assessments. Patients will be analyzed according to the treatment arm to which they were randomized.

Safety Set: The Safety Set consists of all randomized patients who have taken at least 1 dose of study medication. Patients will be analyzed according to the treatment arm for the study drug that they actually received.

Per-Protocol Set: The Per-Protocol Set is defined as all patients from the mITT without any major protocol deviation that could affect the evaluability of the primary efficacy parameter. Patients will be analyzed according to the treatment arm to which they were randomized.

The allocation of patients to analysis sets will be done in a blinded way prior to database lock.

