4.2 Withdrawal of Patients From the Study

Patients will be discontinued from the investigational product and/or from the study in the following circumstances:

1. Enrollment in any other clinical study involving an investigational product or enrollment in any other type of medical research judged not to be scientifically or medically compatible with this study.
2. The patient requests to be discontinued from the study.
3. Sponsor decision to stop the study or to stop the patient's participation in the study for medical, safety, regulatory, or other reasons consistent with applicable laws, regulations, and Good Clinical Practice (GCP).
4. If a clinically significant event occurs that is considered related to the study drug, then the investigational product is to be discontinued and appropriate measures taken. A clinically significant event will be defined as a moderate to severe AE (eg, rash), abnormal clinical sign, or clinical laboratory finding that may pose a risk to the well-being of the patient.

5. The results of the PHQ-9 and C-SSRS indicate a change in mental condition and a risk to the patient by continuing in the study. (see Section 13.2)
6. Certain laboratory test criteria are fulfilled:
 - a. Discontinuation of the investigational product for abnormal liver tests must occur when a patient meets one of the following conditions after consultation with the designated medical monitor:
 - i. Alanine aminotransferase (ALT) or aspartate aminotransferase (AST) $>8 \times$ ULN
 - ii. ALT or AST $>5 \times$ ULN for more than 2 weeks
 - iii. ALT or AST $>3 \times$ ULN and total bilirubin level $>2 \times$ ULN or prothrombin time $>1.5 \times$ ULN
 - iv. ALT or AST $>3 \times$ ULN with the appearance of fatigue, nausea, vomiting, right upper-quadrant pain or tenderness, fever, rash, and/or eosinophilia ($>5\%$)
 1. Liver function tests should be repeated if ALT and or AST $>3 \times$ ULN and/or bilirubin $>1.5 \times$ ULN (or $1.5 \times$ baseline value if baseline value was $>ULN$)

The nature of any conditions, clinical signs or symptoms, or abnormal laboratory values present at the time of discontinuation and any applicable follow-up procedures will be documented. Patients who are discontinued early from the study should complete the Early Termination visit (see Section 6.1). Every effort will be made to follow up all patients for safety.

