5.1 Method of Assigning Patients to Treatment Groups

The study will be conducted in a double-blind manner using a placebo matching the active drug in appearance, labelling, and packaging. Randomization numbers will be assigned according to the randomization schedule that contains patient identification numbers with a corresponding assignment of active drug or placebo. Assignment of study medication as well as site investigational product inventory control and emergency unblinding will be managed by an automated system (Interactive Web Response System).

The randomization ratio of the target 220 patients is 2:2:3:3 (0, 400, 800, 1200 mg dose groups). Thus, 44 patients will each to be randomized to placebo and IX-01 400 mg dose groups, and 66 patients will each to be randomized to IX-01 800 mg and 1200 mg dose groups. The sponsor retains the option to replace any patients who drop out without any postbaseline efficacy data.

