- Patients will return to the study center on Day 56 ± 7 days (Week 8). The patients will be asked for information on any AEs that occurred or are occurring and concomitant medication usage since Visit 4. The patient must return the LogPad. The remaining study medication will be collected. The LogPad will be checked and retained at the study center. (Note: Refer to the Study Training Manual for instructions if a patient does not remember to return the LogPad.)
- The investigator will provide the LogPad back to the patient for completion of the PEP, IIEF, PHQ-9, PGIS and CGIC. After completion, the patient will return the LogPad to the investigator.
- If the results of the PHQ-9 indicate a change in mental condition (or the investigator suspects an adverse change), the investigator should administer the C-SSRS.
- Weight.
- Physical examination.
- Recording of vital sign data (heart rate and blood pressure measurements) and 12-lead ECG.
- Blood sampling for laboratory safety tests (including hematology and clinical chemistry analyses).
- Urinalysis.
- Urine drug screen.
- Adverse events and concomitant medication update.

End of Study Visit 6 (Follow Up)

Patients will return to the study center for a follow-up visit on Day 70 \pm 7 days (Week 10), and the following assessments will be performed approximately 2 weeks after the last visit:

- Weight.
- Physical examination.
- Recording of vital sign data (heart rate and blood pressure measurements) and 12-lead ECG.
- Blood sampling for laboratory safety tests (including hematology and clinical chemistry analyses).
- Urinalysis.
- Adverse events and concomitant medication update.
- C-SSRS, only if clinically indicated per the protocol.

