6.2 Efficacy Assessments

Outcome measures included during treatment include results from the use of the following:

- Stopwatch to measure IELT.
- LogPad (e-diary) to record summary of study drug intake and details of sexual intercourse attempts (including IELT and two PEP questions (control and ejaculation-related personal distress)).
- Responses to the PEP questionnaire.
- Responses to PGIS questionnaire.
- Responses to the CGIC questionnaire.

IELT

The IELT is the time from the start of intercourse (penetration) until ejaculation and is recorded by the patient or partner using the stopwatch provided. At the start of the run-in phase, the patient and partner should decide who will activate the stopwatch and subsequently stop the stopwatch to record the timing of intercourse. The same person should start and stop the stopwatch with every intercourse attempt throughout the study until Visit 5.

LogPad

The LogPad has been specifically designed to enable patients to record details of sexual intercourse attempts and study drug use throughout the study. The key data to be recorded by the patients are date and time of study drug caplets taken, date and time of any intercourse attempt, IELT, level of control of timing of ejaculation; and level of ejaculation-related personal distress. The patient also will use the LogPad at each study visit to complete the PEP, PGIS, IIEF, and PHQ-9 (PEP, PGIS and IIEF are not completed at Visit 3/Week 2). At the final treatment visit (Visit 5 or Early Termination), the CGIC is also collected via the LogPad. For further details of the LogPad design and function, refer to the Study Training Manual.

PEP

The PEP is a widely used self-administered tool that includes measures of perceived control over ejaculation, ejaculation-related personal distress, ejaculation-related interpersonal difficulty, and satisfaction with intercourse. It has been used in many previous studies of PE and is considered validated for this purpose. All of the domains are relevant to a patient with PE, and the instrument has the advantage of being simple and quick to use.¹⁴ In this study an additional exploratory question on bother will be included in the 4-week recall version used at baseline, week 4 and week 8.

PGIS

The Patient Global Impression of Severity is a questionnaire that asks the patient to assess the severity of their condition (categories of response are no PE, mild, moderate, severe).

CGIC

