7.6.1 Analysis of Primary Efficacy Endpoint

[figure not shown]
The primary efficacy analysis of the primary endpoint will be performed on the mITT population. Change from baseline in GM IELT over the treatment assessment period will be analyzed using a mixed linear model, including treatment and baseline IELT as fixed factors and type of site as a random factor.

The primary comparison of interest is IX-01 1200 mg versus placebo. If it is statistically significant at $\alpha=0.05$, then the following comparisons will be tested in the following order:

- IX-01 800 mg vs placebo group
- IX-01 400 mg vs placebo group

An overview of the approach to control for multiple comparisons is provided in Figure 7-1.

Figure 7-1 Overview of the Multiplicity Control

If at any point in the sequence statistical significance is not met, then subsequent analyses in the sequence cannot be deemed statistically significant. In such cases, nominal P values and 95% CI will be reported and interpreted in an exploratory manner. Irrespective of whether there are any statistically significant differences between treatment groups, IELT data from all treatment groups will also be used to model a possible dose response relationship. Further details on dose response analysis will be provided in the SAP.

The analyses above will be repeated using the Per-Protocol and ITT populations to examine the robustness of the primary results.

As a sensitivity analysis of the primary endpoint, a nonparametric approach will be carried out on the mITT population in order to obtain the median treatment effect and 95% CI.

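### Do the differing replacement rules in Sections 5.1 and 7.3 leave the primary analysis short of the 220 men behind the stated power?

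*Combined protocol and SAP*

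**What the plan says.** Section 7.6.1 fixes the population for the main test: "The primary efficacy analysis of the primary endpoint will be performed on the mITT population". Section 7.4 admits a man to that set if he was randomized, took at least one dose and has "at least 2 postbaseline analyzable IELT assessments".

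Section 7.3 gives approximate power of 85% (400 mg), 90% (800 mg) and 90% (1200 mg) for a 45-second difference with an SD of 70 seconds, from "a sample size of 220 patients randomized in total" and split 44/44/66/66. It makes no allowance for loss.

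Two sentences deal with lost men. Section 5.1: "The sponsor retains the option to replace any patients who drop out without any postbaseline efficacy data". Section 7.3, and the synopsis in the same terms: "Additional patients may be recruited if some patients discontinue from the study with less than 2 postbaseline IELT assessments".

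Two other passages affect how Section 5.1 reads. Under Section 4.2, "Patients who are discontinued early from the study should complete the Early Termination visit". At that visit (Section 6.1, Visit 5), "The investigator will provide the LogPad back to the patient for completion of the PEP, IIEF, PHQ-9, PGIS and CGIC". Section 6.2 counts the PEP, PGIS and CGIC among the efficacy measures.

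**The concern.** Section 5.1 is triggered by having no postbaseline efficacy data of any kind, Section 7.3 by having fewer than two IELTs. Early leavers are asked to attend a visit that collects efficacy questionnaires. Read literally, Section 5.1 therefore reaches few men beyond those who skip that visit. Two people working from the two sections could recruit different numbers of extra men.

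Neither trigger is the exact complement of the mITT rule. A man who completes the study with no IELT or only one is outside the mITT Set but has not discontinued. He may also be fully compliant, because Section 6.1 (Visit 2) does not treat fewer than 8 attempts as a deviation. The word analyzable appears in Section 7.4 but not in Section 7.3.

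If enough men fell through, the main test would run on fewer than 220 men, at lower power than stated. The 400 mg comparison, tested last, has the least to spare.

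**Working it through.** **1. The rules side by side.** Each of these men is outside the mITT Set.

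| Man | Section 5.1 trigger | Section 7.3 trigger |
|---|---|---|
| Leaves with no efficacy data at all | yes | yes |
| Leaves with no IELT, completes the final questionnaires | no | yes |
| Leaves with exactly one IELT | no | yes |
| Leaves with two or more IELTs, fewer than two analyzable | no | no |
| Completes with no IELT or one | no | no |
| Never dosed, leaves with two or more IELTs | no | no |

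Section 7.3 covers everyone whom Section 5.1 covers, and more. Among men who discontinue, its count of fewer than two is the complement of the mITT count, apart from the word analyzable and the dose requirement.

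**2. The plan's own power.** Inputs from Section 7.3: difference 45 s, SD 70 s, two-sided alpha 0.05, 44/44/66/66. SE = 70 × √(1/n₁ + 1/n₂); power ≈ Φ(45/SE − 1.960).

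- 400 mg: SE = 70 × √(1/44 + 1/44) = 14.92; 45/14.92 = 3.015; power 0.854.
- 800 and 1200 mg: SE = 70 × √(1/44 + 1/66) = 13.62; 45/13.62 = 3.303; power 0.910.

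A noncentral t with 220 − 4 = 216 degrees of freedom gives 0.851 and 0.908. The stated figures are reproduced.

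**3. Power if men are lost and not replaced.** The documents give no loss rate, so this is an assumed range, equal across arms, using the same formula with each n multiplied by (1 − loss).

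| Loss | Men analyzed | 400 mg | 800 and 1200 mg |
|---|---|---|---|
| 2% | about 216 | 0.847 | 0.905 |
| 5% | 209 | 0.836 | 0.896 |
| 10% | 198 | 0.816 | 0.880 |
| 15% | 187 | 0.794 | 0.861 |
| 20% | 176 | 0.769 | 0.840 |

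Up to 5% loss, every figure is within 2 points of the stated value. The 400 mg comparison drops below 0.80 at about 14%.

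**4. What the earlier trial suggests.** Section 1.3.5 reports 88 men recruited to IX-0103. Its percentages imply these denominators:

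- Maximum dose taken: 50/0.893 = 56 and 23/0.767 = 30; 86 of 88, about 2% without dose data.
- PEP control: 17 at 33% implies 51 or 52; 1 at 3% implies 29 or 30 if placebo is capped at 30; 80 to 82 of 88, 7% to 9% missing.
- PEP distress: 24/0.46 = 52 and 4/0.16 = 25; 77 of 88, 12.5% missing.
- CGIC: 21/0.44 = 48 and 3/0.13 = 23; 71 of 88, 19% missing.

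The last three measure missing final questionnaires, not fewer than two IELTs. Men in that trial took a mean of 14.6 (IX-01) and 13.0 (placebo) doses, although the range starts at 1. A man who leaves early after two analyzable attempts on treatment stays in the mITT Set.

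**5. Whether recruiting to 220 mITT men would secure the power.** Randomizing 220/(1 − loss) means 245 men at 10% loss and 273 at the CGIC-based 19.3% (17 of 88). Now suppose retention by arm as for CGIC: 23/30 = 0.767 on placebo and 48/56 = 0.857 on active drug. The 2:2:3:3 weights become 1.533, 1.714, 2.571 and 2.571, which sum to 8.390. Scaled to a total of 220, the arms hold about 40/45/67/67. Power (noncentral t) is then 0.84 for 400 mg and 0.89 for the higher doses, so a pooled count would not restore the planned figures exactly either.

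**The case for a change.** The strongest case for acting is that replacement happens during recruitment, while membership of the analysis sets is settled only before database lock. A later analysis plan therefore cannot repair a vague recruitment rule. The trial exists to compare doses, 400 mg has the thinnest margin, and a loss of 15% would take it to 0.79. Repeating the analysis on the ITT Set does not recover the loss, because a man without a postbaseline IELT has no change value unless one is imputed. Better wording costs almost nothing.

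Much of this stands as description: the triggers differ, the sample size has no inflation, and completers with too few IELTs are covered by neither rule. It does not show harm. Identical triggers would not secure 220 men, because both sentences only permit replacement. The sponsor can already act on the wider rule. No document shows that completers with no IELT or one occur in any number; entry requires at least four run-in attempts and willingness to make at least eight more. The 15% to 20% range rests on missing final questionnaires, of which CGIC is the worst case. Defining analyzable to include undosed attempts would decide what is being estimated for an on-demand drug, which is debatable and separate from replacement.

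**Conclusion.** The mismatch is a drafting inconsistency between two permissive sentences, and it leaves the plan sound. Section 7.3 states power for 220 randomized men, says approximately, and is arithmetically right. It makes no promise about the size of the mITT Set. With no loss rate in the documents, no stated figure can be shown to be missed. Under equal loss without replacement, the first-tested comparison (1200 mg) keeps about 0.90 at 5%, 0.88 at 10% and 0.86 at 15%; 400 mg has about 0.84, 0.82 and 0.79.

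A sponsor who wants extra men can recruit them under Section 7.3 as written for most early leavers outside the mITT Set. Using that trigger in Section 5.1 too would be tidier but would alter no analysis. A binding target of 220 mITT men would trade a known increase in enrolment, 25 men at 10% loss, for a few points of power against an unknown loss. Leaving that to the sponsor's discretion is a fair choice in a Phase 2b dose-finding trial. The meaning of analyzable is a detail that the analysts can settle blinded when the sets are allocated, as Section 7.4 provides.

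This conclusion rests on the planning SD and difference, on roughly equal loss across arms, and on a loss not far above 10%.
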